## **6.2.1 Study Treatment Administration on Week 1 Day 1 (W1D1)**

### Nivolumab and Ipilimumab:

Doses of nivolumab (3 mg/kg) will always be administered IV at the clinic by infusion on Day 1 of each 21-day cycles for the first 4 doses. Thereafter, doses (480 mg) will be administered on Day 1 of each 28-day cycle. In this study, treatment with nivolumab will be given for a maximum of 2 years from the start of study treatment.

Doses of ipilimumab (1 mg/kg) will always be administered IV at the clinic by infusion on Day 1 of each 21-day cycles for a maximum of four doses. Cycles may be longer if nivolumab or ipilimumab treatment is delayed due to toxicity or other reasons.

When nivolumab and ipilimumab are to be administered on the same day, nivolumab is to be administered first. Nivolumab infusion (approximately 30 minutes) must be promptly followed by a saline flush to clear the line of nivolumab before starting the ipilimumab infusion. The second infusion will always be ipilimumab study drug (approximately 30 minutes infusion) and will start after the infusion line has been flushed and participant has been observed to ensure no infusion reaction has occurred. The time in between infusions is expected to be approximately 30 minutes (from the end of the nivolumab infusion to the start of the ipilimumab infusion).

CONFIDENTIAL

Protocol XL184-313 Protocol Amendment 3.0  
Page 81 of 193

On W1D1, nivolumab and ipilimumab are to be administered before the oral study treatment.

The infusion of nivolumab and ipilimumab will be prepared according to the local prescribing information or the pharmacy manual. The IV administration of nivolumab and ipilimumab can only occur in a clinical setting with staff experienced in managing of infusion-related reactions and with access to emergency services.

Subjects should be carefully monitored for infusion reactions during IV administration. If an acute infusion reaction is noted, participants should be managed according to [Section 6.6.3](#).

**Cabozantinib/Placebo:**

The subject will be fasted (with the exception of water) for at least 2 hours before receiving cabozantinib/placebo. Upon completion of the 2-hour fast, the subject will receive the oral dose of cabozantinib/placebo with a minimum of 8 oz (240 mL) of water in the clinic.

- After taking cabozantinib/placebo, the subject will continue to fast for a further 1 hour while under observation to monitor for potential AEs.
- If the subject develops an infusion reaction, the administration of oral study treatment will be delayed or interrupted until the subject has recovered and the Investigator believes that it is safe to administer cabozantinib/placebo.

For cabozantinib/placebo dosing on subsequent dosing days refer to [Section 6.2.2](#).

**6.2.2 Cabozantinib/Placebo Administration outside the Clinic**

The subject should take cabozantinib/placebo outside the clinic at approximately the same time every day, preferentially before going to bed, and should adhere to the fasting requirements described in this section.

Subjects should fast (with the exception of water) for at least 2 hours after eating the evening meal before taking their dose. After the 2-hour fast and before going to bed, subjects are to take cabozantinib/placebo with a full glass of water (minimum of 8 oz or 240 mL) with no food intake for one hour post-dose. If the subject's schedule requires taking cabozantinib/placebo during the day, the subject is to be instructed to follow the same fasting recommendations.

Tablets should not be crushed or chewed. Grapefruit and Seville oranges (and products made from them) should be avoided while being treated with cabozantinib/placebo.

CONFIDENTIAL

Protocol XL184-313 Protocol Amendment 3.0  
Page 82 of 193

Subjects are to be instructed to not make up vomited doses and to maintain the planned dosing schedule. Subjects are not to make up for missed doses if more than 12 hours have elapsed after the time the subject would usually take cabozantinib/placebo. In the event of missed doses, subjects are not to take 2 doses to make up for the one the subject missed.

Any unused study treatment must be returned to the study site for drug accountability and disposal.

### **6.3 Treatment After Study Completion**

After study completion (see [Section 3.6.3](#)), subjects who continue to demonstrate clinical benefit may be eligible to receive Exelixis-supplied study treatment for the maximum treatment duration specified in [Section 6.2](#) during the Maintenance Phase. Alternatively, study treatment may be provided via a rollover study requiring approval by responsible health authority and ethics committee or through another mechanism at the discretion of Exelixis.

Exelixis reserves the right to terminate access to Exelixis-supplied study treatment if any of the following occur:

- a) the study is terminated due to safety concerns;
- b) the development of nivolumab, ipilimumab, or cabozantinib is terminated for other reasons, including but not limited to lack of efficacy and/or not meeting the study objectives (eg, study is declared futile or the null hypothesis is not rejected for the primary endpoint of PFS);
- c) the participant can obtain medication from a government-sponsored or private health program.

In all cases Exelixis will follow local regulations. Exelixis will work with study investigators to act in the best interest of subjects.

### **6.4 Compliance**

Subject compliance with outpatient study treatment will be assessed by the site using drug dispensing and return records, infusion logs, progress notes about dose reductions/interruptions, and subject interview. These data will not be directly recorded in the CRF; rather, the CRF will capture infusion details and, for oral study treatment, intervals of constant dose and reasons for changes in dose level (eg, a new record completed each time dose level changes, including periods where no dose was taken, and the reason for a dose level change).

CONFIDENTIAL

Protocol XL184-313 Protocol Amendment 3.0  
Page 83 of 193

## **6.5 Study Treatment Accountability**

The Investigator or designee will maintain accurate records of receipt of all study treatment including dates of receipt. In addition, accurate records will be kept regarding when and how much study treatment is dispensed and used by each subject in the study. Reasons for deviation from the expected dispensing regimen must also be recorded. Drug accountability will be performed periodically by the Sponsor or designee at interim monitoring visits. At completion of the study, to satisfy regulatory requirements regarding drug accountability, all unused study treatment will be reconciled and destroyed according to applicable state, federal, and local regulations.

## **6.6 Safety Considerations**

Subjects will be monitored for SAEs from the time of signing informed consent and for nonserious AEs from first dose of study treatment. Monitoring continues through 100 days for unrelated SAEs ([Table 8-1](#)) after the date of the decision to permanently discontinue all study treatment (defined as the later of the date of the decision to discontinue all study treatment or the date of the last dose of any study treatment). Longer monitoring periods are required for related SAEs and certain other events as described in [Section 8.3](#). Further details for follow-up and data collection requirements for AEs, SAEs, and AESIs are summarized in [Appendix H](#). Subjects will be instructed to notify their physician immediately for any occurring AE. Causality assessment of AEs should include at minimum confounding factors such as disease and concomitant medications. Adverse event severity will be graded by the Investigator according to CTCAE v5.

The following should be taken into consideration in decisions regarding management for treatment-related side effects: cabozantinib, nivolumab, and ipilimumab have class-specific safety profiles based on their mechanisms of action but may also cause AEs that overlap.

- Examples of VEGFR-TKI associated AEs caused by cabozantinib are hypertension and hand-foot syndrome.
- Examples of irAEs caused by nivolumab are pneumonitis, colitis, hepatitis, nephritis, skin reactions, encephalitis, and endocrinopathies.
- Examples of irAEs caused by ipilimumab are hepatitis, endocrinopathies and hypophysitis.
- Examples of overlapping AEs are diarrhea and elevations in liver function tests (transaminases, bilirubin; see [Section 6.6.1](#)).

CONFIDENTIAL

Protocol XL184-313 Protocol Amendment 3.0  
Page 84 of 193

- As a general approach, all AEs should be managed with supportive care including both pharmacological and non-pharmacological treatments according to consensus management guidelines at the earliest signs of toxicity considered related to study treatment.
- Study treatment may be continued for mild AEs if appropriate supportive care has been initiated to ameliorate symptoms. Should this be ineffective and toxicities become unacceptable, dose modifications of study treatment should be considered to prevent worsening of toxicity. Moderate to severe AEs usually require dose modifications including dose reductions and/or interruptions.
- Dose interruptions of cabozantinib/placebo, nivolumab, or ipilimumab for AEs may occur at any time and independently at the discretion of the Investigator (for hepatocellular toxicity see below). If all study treatment is interrupted for more than 12 weeks, treatment should be discontinued unless approved by the Sponsor.
- In the case of AEs of *hepatocellular toxicity*, the Investigator should follow the guidance provided in [Section 6.6.1](#), which summarizes the dose modification guidance for BOTH cabozantinib/placebo treatment as well as nivolumab/ipilimumab treatment.
- In the case of AEs of *non-hepatocellular toxicity*, the Investigator should follow the guidance on dose modifications of cabozantinib/placebo treatment in [Section 6.6.2](#), and on dose modifications of nivolumab and ipilimumab in [Section 6.6.3](#) with more detailed guidance in [Appendix E](#).

#### **6.6.1 Management of Hepatocellular Toxicity Associated with Cabozantinib/Placebo and Nivolumab/Ipilimumab**

Elevations of aminotransferases (ALT and AST) and bilirubin have been observed during treatment with cabozantinib, nivolumab, and ipilimumab. It is recommended that subjects with elevation of ALT, AST, and/or bilirubin have more frequent laboratory monitoring of these parameters. If possible, hepatotoxic concomitant medications should be discontinued in subjects who develop increased values of ALT, AST, or bilirubin, and other causes (eg, cancer-related, infection) should be evaluated.

CONFIDENTIAL

Protocol XL184-313 Protocol Amendment 3.0  
Page 85 of 193

The following condition requires discontinuation of all study drugs:

- Drug-related ALT or AST  $> 3 \times$  ULN in combination with total bilirubin  $> 2 \times$  ULN without reasonable other explanation, consistent with drug-induced liver injury (DILI).

[Table 6-3](#) provides suggested guidance on management of hepatotoxicity related to cabozantinib/placebo and nivolumab/ipilimumab.

In the event cabozantinib/placebo is interrupted and nivolumab/ipilimumab delayed due to an increase of serum ALT or AST  $> 3.0 \times$  ULN **or** serum total bilirubin  $>$  ULN to  $1.5 \times$  ULN, nivolumab and (if fewer than 4 ipilimumab doses have been administered and no AE has occurred that led to discontinuation of ipilimumab alone) ipilimumab should be resumed upon return of liver function tests to baseline grade, at which time cabozantinib/placebo should be resumed with a dose reduction (from either two tablets per day to one tablet per day, or one tablet per day to one tablet every other day, as appropriate).

If no additional ipilimumab is to be administered, the dose of cabozantinib/placebo should be re-escalated from one tablet per day to two tablets per day no sooner than 10 days after resumption of blinded oral therapy. Alternatively, if the subject had been taking one tablet every other day, then the dose of cabozantinib/placebo may be re-escalated to one tablet every day and, if tolerated, then to two tablets per day no sooner than 14 days thereafter.

Consult with the medical monitor to discuss further management should rechallenge be followed by any recurrence of increased liver function tests.

Dose delays should not alter the timing of other study assessments, including but not limited to tumor imaging scheduled based on W1D1 ( $\leq 3$  days after randomization).

For additional information on dose modifications of nivolumab/ipilimumab treatment, refer to [Section 6.6.3](#) and [Appendix E](#).

CONFIDENTIAL

Protocol XL184-313 Protocol Amendment 3.0  
Page 86 of 193

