**Table 6-3: Suggested Management of Hepatotoxicity Associated with Study Treatment**

Severity of LFT a Elevations by Laboratory Value	Dose Modification Guidance b	Management/Follow-up Guidance
AST or ALT > ULN to 3.0 x ULN and/or total bili > ULN to 1.5 x ULN, regardless of baseline value	
 
Cabozantinib: 
 
Continue cabozantinib per protocol
 
 
 
Nivolumab /Ipilimumab: 
 
Continue therapy per protocol
 
 
 
	
 
Monitor LFTs per protocol.
 
Discontinue concomitant hepatotoxic medications, if possible.
 

AST or ALT > 3.0 x ULN to $\leq$ 5 x ULN or total bili > 1.5 x ULN to $\leq$ 3 x ULN, regardless of baseline value	
 
Cabozantinib: 
 
Interrupt cabozantinib dosing.
 
If LFTs return to baseline grade, resume cabozantinib at a reduced dose. After completion of ipilimumab regimen, re-escalate cabozantinib dose as per protocol. If no additional ipilimumab doses are to be administered, the dose of cabozantinib may be re-escalated no sooner than 10 days after re-initiation of cabozantinib.
 
See Section 6.6.1 for additional guidance.
 
 
 
Nivolumab /Ipilimumab: 
 
Delay therapy per protocol.
 
If LFTs return to baseline grade, resume therapy per protocol.
 
 
 
	
 
Monitor LFTs twice weekly or more frequently as deemed clinically necessary. 
 
If tapering off steroid therapy, monitor LFTs once weekly or more often per clinical judgmentc.
 
If LFTs return to baseline grade, resume with routine monitoring.
 
 
 
If LFT elevations persist > 3 days or worsen: 
 
Administer 0.5-1 mg/kg/day methylprednisolone or oral equivalent.
 
When LFTs return to baseline grade or CTCAE Grade <math>\leq</math> 1, taper steroids over at least 1 monthc.
 
Consider prophylactic antibiotics for opportunistic infections.
 
 
 

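### The Section 6.6.1 liver restart sentence pairs Table 6-3's interrupt threshold for ALT/AST with the bilirubin range in which that table continues all drugs, and it sets no upper ALT/AST limit

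*Protocol*

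**What the plan says.** Protocol Section 6.6 sends investigators to Section 6.6.1 for hepatocellular toxicity. That section has running text and Table 6-3, and both cover the oral drug and the two infusions.

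**The restart sentence in the text.** It opens "In the event cabozantinib/placebo is interrupted and nivolumab/ipilimumab delayed due to an increase of serum ALT or AST" above 3.0 × ULN, or total bilirubin above ULN up to 1.5 × ULN. Nivolumab is then to be resumed. If fewer than four doses have been given and ipilimumab has not been stopped by itself because of an event, "ipilimumab should be resumed upon return of liver function tests to baseline grade, at which time cabozantinib/placebo should be resumed with a dose reduction" of one tablet step. When no ipilimumab remains to be given, the oral dose is to be "re-escalated from one tablet per day to two tablets per day no sooner than 10 days after resumption of blinded oral therapy".

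**Table 6-3.**
- The first row includes "total bili > ULN to 1.5 x ULN, regardless of baseline value". The instruction is "Continue cabozantinib per protocol" for the oral drug and "Continue therapy per protocol" for the infusions.
- The second row starts at ALT/AST above 3.0 × ULN or "total bili > 1.5 x ULN to" 3 × ULN. The instruction is "Interrupt cabozantinib dosing" and delay the infusions. The row then gives its own rule for resuming at a reduced dose and re-escalating, and refers back to Section 6.6.1 for more guidance.
- The third row starts at ALT/AST above 5 × ULN or bilirubin above 3 × ULN. The oral drug is discontinued above 8 × ULN (ALT/AST) and otherwise resumed only with Sponsor approval. The infusions are delayed or stopped. A note adds that most cases above 5 × ULN end study treatment permanently, and that resuming needs the Medical Monitor's approval.

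**The concern.** Two parts of one section give different signals for the same laboratory value. At bilirubin 1.2 × ULN the table says to carry on with everything, while the text lists that value among the reasons drugs were held. A site that takes the sentence as describing when drugs are held could interrupt three drugs and restart the oral one at half dose, although the table calls for no change.

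A second problem runs in the other direction. The sentence puts no ceiling on ALT/AST, yet says that drugs should be resumed once tests return to baseline grade. Read alone, it covers values for which the third row demands discontinuation or approval.

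Liver events are expected with this regimen. Section 6.6 lists raised liver tests as an overlapping toxicity, and Section 1.6 reports that raised ALT led to discontinuation in 4 of 44 subjects on an earlier triplet arm. The rule is likely to be used.

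**Working it through.** No sample size, power or alpha figure is involved. The check is a side-by-side reading of the current protocol text (Amendment 3.0).

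| Source | ALT/AST (× ULN) | Total bilirubin (× ULN) | Action |
|---|---|---|---|
| Section 6.6.1 restart sentence | > 3.0, no upper limit | > 1.0 to 1.5 | Presupposes a hold; resume at baseline grade, oral dose reduced |
| Table 6-3, first row | > 1.0 to 3.0 | > 1.0 to 1.5 | Continue all drugs |
| Table 6-3, second row | > 3.0 to 5 | > 1.5 to 3 | Interrupt oral drug, delay infusions, resume at baseline grade with oral dose reduced |
| Table 6-3, third row | > 5 | > 3 | Discontinue, or resume only with approval |

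**Step 1: bilirubin.** The sentence's range equals the first row's and overlaps neither the second nor the third. All of it lies where the table continues treatment. This assumes that ALT/AST is not itself above 3.0 × ULN.

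**Step 2: which side is wrong.** The protocol does not say, so this is an inference.
- The sentence's ALT/AST limit is where the second row starts.
- Its restart rule (return to baseline grade, reduced oral dose, re-escalation after at least 10 days) is the second row's.
- The second row cross-refers to Section 6.6.1.
- Inclusion criterion 8f admits subjects with bilirubin up to 1.5 × ULN, so a subject may enter within the range that the sentence names.

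Only the bilirubin range comes from another row. The intended text was most plausibly above 1.5 × ULN.

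**Step 3: ALT/AST ceiling.** Above 3.0 × ULN with no limit includes values above 5 and above 8 × ULN. The sentence has drugs resumed there; the third row does not allow that without approval, and above 8 × ULN it ends the oral drug.

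**Step 4: dose at stake if a site acts on the bilirubin range.** For a subject on full dose, two 20 mg tablets become one: 2 × 20 = 40 mg/day falls to 1 × 20 = 20 mg/day, and 20/40 = 50%. With no ipilimumab left, the shortest reduced period is 10 days: 10 × 20 = 200 mg taken instead of 10 × 40 = 400 mg. Days on hold come on top. This is plain halving of the label dose, not an estimate of exposure lost in the trial.

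**The case against.** The strongest reply is that the sentence decides nothing about holding drugs. It begins from a hold that has already happened and governs restart. The decision to hold sits in Table 6-3, whose first two rows are clear. Harm requires a site to read a conditional clause as an order and to set aside an explicit instruction to continue in the same section. This largely stands: a reader might infer that the protocol orders interruption at bilirubin just above ULN, and the text does not say so.

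A reader might also infer that subjects at 1.5 to 3 × ULN have no restart rule. The second row gives them one. What they lack is a match in the sentence to which that row sends them, where the conditions for resuming ipilimumab and the tablet steps are spelled out.

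The bilirubin misreading errs toward less drug, with re-escalation provided for. That stands too. It does not cover the open ALT/AST limit, which read literally errs toward more drug. There the reply is that the third row is in the same table, that the stop rule for drug-induced liver injury is stated separately, and that recurrence after rechallenge goes to the medical monitor. These reduce the risk without making the sentence agree with the table. The table is also headed as suggested management, so its precedence over the text is not explicit.

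**Conclusion.** Wrong as written, minor. The mismatch itself is certain: one bilirubin range is taken from the wrong row, and the ALT/AST condition has no upper bound. That the sentence rather than the table is at fault is a well-supported inference. The consequence is conflicting guidance to sites. At worst, on the bilirubin side, drugs are held needlessly for a mild rise and the oral drug restarts at 20 instead of 40 mg/day.

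The documents give no count of subjects affected, and nothing here bears on power, alpha or the PFS and OS analyses. A reader might be tempted to project a long reduced-dose period across the remaining ipilimumab doses on their scheduled dates. The documents do not support that, because the sentence applies only when the infusions have been delayed.

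**What to change.** In the Section 6.6.1 restart sentence, change the bilirubin condition to total bilirubin above 1.5 × ULN. Add one sentence stating that above 5 × ULN (ALT or AST) or 3 × ULN (total bilirubin) the discontinuation and approval rules of Table 6-3 apply. The addition is needed for bilirubin as well, since the corrected condition would otherwise also be open-ended. Leave the drug-induced liver injury rule as it is.

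The cost is one threshold and one sentence in the next amendment, with the IRB/EC approval that Section 14 requires. There is no data or sample-size cost.

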AST or ALT > 5 x ULN or total bili > 3 x ULN, regardless of baseline value	
 
Cabozantinib: 
 
Discontinue cabozantinib if ALT or AST > 8 x ULN.
 
Otherwise interrupt cabozantinib dosing and resume at a reduced dose after LFTs return to baseline grade (Sponsor approval required)
 
 
 
Nivolumab /Ipilimumab: 
 
Delay dose or permanently discontinue.
 
 
 
	
 
Monitor LFTs twice weekly or more frequently as deemed clinically necessary.
 
During steroid taper, monitor LFTs once weekly or more often per clinical judgmentc.
 
For AST or ALT > 5 x ULN to <math>\leq</math> 20 x ULN, or total bilirubin > 3 x ULN to <math>\leq</math> 10 x ULN: 
 
Administer 1.0-2.0 mg/kg/day methylprednisolone IV or IV equivalent.
 
 
 
For AST or ALT > 20 x ULN, or total bilirubin > 10 x ULN: 
 
Administer 2.0 mg/kg/day methylprednisolone IV or IV equivalent.
 
 
 

CONFIDENTIAL

Severity of LFT a Elevations by Laboratory Value	Dose Modification Guidance b	Management/Follow-up Guidance
	
* In most cases of AST or ALT <math>> 5 \times</math> ULN, study treatment will be permanently discontinued. If the investigator determines a possible favorable benefit/risk ratio that warrants continuation of study treatment, a discussion between the investigator and the Medical Monitor/ designee must occur and approval from Medical Monitor prior to resuming therapy must be obtained.
	
 
• Add prophylactic antibiotics for opportunistic infections.
 
• Consult Gastroenterologist.
 
• If LFT elevations do not improve in <math>> 3</math> days, worsen or rebound: 
 
– Add mycophenolate mofetil 1g BID.
 
– If no response within an additional 3-5 days, consider other immunosuppressants per local guidelines.
 
 
 
• Dosing may resume when laboratory values return to baseline.
 
• Taper steroids over at least 1 monthc.
 

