### 8.7.2. Analysis

All laboratory data parameters and visits will include flags for values above or below laboratory reference ranges. Toxicity grades will be assigned programmatically by applying the CTCAE v5.0 guidelines. Only results with assessment dates through the end of the standard safety observation period (see [Section 4.5](#)) will be tabulated in summary tables.

Laboratory summaries will be presented in SI units. Continuous laboratory test results will be summarized by treatment group using descriptive statistics for actual values and for changes from baseline by scheduled visit. Plots showing mean and standard error at each scheduled visit (with visits shown on x-axis) may also be presented for some laboratory parameters. For test results which are below or above the quantification level, the imputed values as described in [Appendix C](#) will be used for deriving the grade and then summarized.

Tables summarizing baseline laboratory values and the incidence of laboratory abnormalities by baseline and maximum post-baseline CTCAE grade over all records will be presented. In addition, the following summaries will also be presented:

A. Liver function abnormalities will be assessed as follows:

- Shift from baseline based on normal ranges

- Summaries of subjects meeting Hy's Law laboratory screening criteria as shown below:
  - $> 3 \times \text{ULN}$  (ALT or AST),  $> 2 \times \text{ULN}$  Total Bilirubin, and  $< 2 \times \text{ULN}$  ALP
  - $> 3 \times \text{ULN}$  (ALT or AST),  $> 2 \times \text{ULN}$  Total Bilirubin, and  $\geq 2 \times \text{ULN}$  ALP
  - $> 3 \times \text{ULN}$  (ALT or AST),  $> 2 \times \text{ULN}$  Total Bilirubin

B. For renal failure surveillance, a summary of subjects meeting renal failure laboratory screening criteria as shown below will be provided:

- Serum creatinine  $\geq 3.0 \times \text{ULN}$  and  $\geq 2.0 \times$  baseline value or
- Estimated Glomerular Filtration Rate (eGFR)  $\leq 50\%$  of the baseline value or
- eGFR  $< 30 \text{ mL/min/1.73 m}^2$  and  $\geq 25\%$  reduction from the baseline value

$$\text{eGFR} = 186 \times (\text{Creatinine in mmol per L} / 88.4)^{-1.154} \times (\text{Age})^{-0.203} \times (0.742 \text{ if female}) \times (1.210 \text{ if black}) \quad [\text{from website: } \text{https://ukidney.com/nephrology-resources/egfr-calculator}]$$

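### Minor: three printed safety thresholds conflict with the documents' own values (the bilirubin band in the Protocol 6.6.1 resume rule, and the SI equivalents of UPCR 1 mg/mg in SAP 8.7.1 and Protocol Table 6-9)

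*Protocol*

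**What the plan says.** **Liver tests.** One sentence in Protocol Section 6.6.1 covers restarting after cabozantinib/placebo has been interrupted and nivolumab/ipilimumab delayed. The hold may be for ALT or AST above 3.0 x ULN, or for "serum total bilirubin $>$ ULN to $1.5 \times$ ULN, nivolumab and (if fewer than 4 ipilimumab doses have been administered". Drugs restart once liver tests return to baseline grade, with cabozantinib/placebo at a reduced dose. Table 6-3, in the same section, sets the actions by band:

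- Row 1 includes "total bili > ULN to 1.5 x ULN, regardless of baseline value". Cabozantinib, nivolumab and ipilimumab all continue.
- Row 2 includes "total bili > 1.5 x ULN to $\leq$ 3 x ULN". Cabozantinib is interrupted and nivolumab/ipilimumab delayed. The row has its own short restart rule and refers back to Section 6.6.1 for more.
- Row 3 includes "total bili > 3 x ULN, regardless of baseline value". The nivolumab/ipilimumab action is "Delay dose or permanently discontinue".

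**UPCR.** SAP Section 8.7.1 defines sponsor grades in both units and prints the grade 1/2 boundary of 1.0 mg/mg as 121.0 mg/mmol in two lines. SAP Section 8.7.2 adds: "Laboratory summaries will be presented in SI units". It does not say which unit drives the sponsor-defined grading. Protocol Table 6-9 prints 1 mg/mg as 113.1 mg/mmol in row 1, but gives the lower bound of row 2 (also 1 mg/mg) as 226.2 mg/mmol. Inclusion criterion 8h prints 1 mg/mg as 113.2 mg/mmol.

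**The concern.** These are operative numbers for dose guidance and laboratory grading, not background text.

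Section 6.6 directs investigators to 6.6.1 for hepatocellular toxicity, and row 2 of Table 6-3 points there again. A subject held for bilirubin above 1.5 and up to 3 x ULN is thus sent to a paragraph that does not name that band. Yet that paragraph carries the condition on remaining ipilimumab doses and the tablet-by-tablet reduction. The band it does name is one in which the table holds nothing.

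For UPCR, a single boundary has two different values depending on the unit read. In the SAP this could move some results down one grade. In Table 6-9 it leaves a range of SI values that belongs to no row.

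**Working it through.** **Bilirubin bands (x ULN), set side by side**

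- Section 6.6.1 resume sentence: above 1.0 to 1.5
- Table 6-3 row 1 (continue all drugs): above 1.0 to 1.5
- Table 6-3 row 2 (hold): above 1.5 to 3
- Table 6-3 row 3 (hold or stop): above 3

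The sentence matches row 1 exactly and overlaps rows 2 and 3 nowhere. Its ALT/AST part starts at 3.0 x ULN, which is where row 2 starts. That suggests row 1's bilirubin limits were printed where a hold threshold was meant.

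**UPCR conversion.** The factor is the SI value divided by the mg/mg value, taken from every pair in the documents.

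| Source | mg/mg | mg/mmol | Factor |
|---|---|---|---|
| Inclusion criterion 8h | 1 | 113.2 | 113.2 |
| Table 6-9 row 1 | 1 | 113.1 | 113.1 |
| Table 6-9 row 2 upper, row 3 | 3.5 | 395.9 | 113.11 |
| SAP grade 1 lower | 0.15 | 17.0 | 113.3 |
| SAP grade 2 upper, grade 3 | 3.5 | 396.0 | 113.14 |
| **SAP grade 1/2 boundary** | 1.0 | 121.0 | **121.0** |
| **Table 6-9 row 2 lower** | 1 | 226.2 | **226.2** |

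Five of the seven pairs agree to within rounding; two do not. Converting those two back with 113.1:

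- SAP: 121.0 / 113.1 = 1.07 mg/mg, about 7% too high. The affected interval is 121.0 - 113.1 = 7.9 mg/mmol wide, and 7.9 / 113.1 = 0.07 mg/mg.
- Table 6-9: 226.2 / 113.1 = 2.00 mg/mg, twice the labelled value. Row 1 ends at 113.1 and row 2 starts above 226.2, so values above 113.1 and up to 226.2 mg/mmol fall in no row on the SI scale.

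After correction, SAP grade 1 runs from 17.0 to 113.1 mg/mmol and grade 2 starts above 113.1. Row 2 of Table 6-9 runs from above 113.1 to below 395.9.

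**The case against.** The best defence is that none of the three slips forces a wrong action.

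- The 6.6.1 sentence is conditional. It orders no hold and sets no threshold, and Table 6-3, titled as suggested management, carries every hold threshold. Row 2 has its own restart rule, so no subject lacks guidance. If a drug were held at 1.0 to 1.5 x ULN, waiting for baseline grade and restarting at a reduced dose would be the cautious course.
- In Table 6-9 every action is written in mg/mg or g per 24 hours, and the SI figures are only row labels. No dose change is required up to 2 mg/mg. Only an optional 24-hour urine confirmation falls in the affected range.
- In the SAP the correct mg/mg limit is printed beside 121.0. The cut-off is the same in both arms, SAP Section 8 plans no formal safety comparison between arms, and investigators grade adverse events separately under CTCAE.

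All of this stands, and it is why the point is minor. It does not reconcile the printed values.

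A reader might go further. The ALT/AST condition in the same sentence has no upper limit, so the sentence may seem to permit restarting after values above 5 x ULN without the approvals that row 3 demands. The documents do not support that reading. Table 6-3 is part of Section 6.6.1, so both approvals are printed there: cabozantinib may "resume at a reduced dose after LFTs return to baseline grade (Sponsor approval required", and above 5 x ULN for AST or ALT "approval from Medical Monitor prior to resuming therapy must be obtained". The sentence applies only to treatment that was interrupted or delayed, so it does not reach subjects whose treatment was discontinued. Row 3 stops cabozantinib above 8 x ULN for ALT or AST and expects permanent discontinuation of study treatment in most cases above 5 x ULN for either. For the few who may restart, row 3 adds a condition to the general rule; it does not contradict it.

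**Conclusion.** The point holds as three printing errors, each wrong as written and each minor.

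- **Section 6.6.1:** the bilirubin band named for restarting has zero overlap with the table's hold bands. This is an inconsistency in dose guidance; no harm is shown.
- **SAP 8.7.1:** the grade 1/2 boundary is 7.9 mg/mmol (0.07 mg/mg) too high. Under-grading follows only if the SI cut-off is the one programmed. That is an assumption: SI presentation makes it plausible, but the SAP does not state it. Grade 3 is unaffected.
- **Table 6-9:** the SI lower bound of row 2 is double its label, with no effect on any mandatory dose action.

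The documents do not show how many subjects have values in the affected ranges. No efficacy, power or alpha figure changes.

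**What to change.** - **Protocol 6.6.1:** change the bilirubin condition to above 1.5 x ULN, where Table 6-3 holds begin. Leave the ALT/AST condition as it is, and leave row 3's approvals to the table. Adding upper caps to the sentence is not advised: it could remove restart detail (the ipilimumab dose condition and the tablet steps) for row 3 subjects who are allowed to resume.
- **SAP 8.7.1:** change 121.0 to 113.1 mg/mmol in the grade 1 and grade 2 lines.
- **Protocol Table 6-9, row 2:** change the SI lower bound from 226.2 to 113.1 mg/mmol.

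The cost is one limit in a sentence, one table entry and one boundary printed twice. SAP Section 4.8 already allows minor corrections by addendum. Protocol Section 14 generally requires ethics approval before changes take effect, so the two protocol items fit best in the next amendment. No new data are needed.
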